As of January 2024, EPS SURA manages a cohort of approximately 15,300 HIV patients. The control, evaluation, and follow-up of these patients are primarily conducted by specialized healthcare institutions (IPS), with a smaller proportion monitored by affiliated IPS providers. Program indicators include treatment abandonment rates, virological success rates, virological success with ART in the last 3 months, HIV viral load, and CD4 T-lymphocyte levels in the past 6 months for patients with HIV. To assess patient adherence, regular weekly evaluations are conducted, which include laboratory monitoring and attendance at medical appointments. In cases of non-compliance, a strict follow-up plan is established by a designated physician and a pharmaceutical chemist to verify medication intake and evaluate risk factors associated with non-adherence on an individual basis. From 2020 to 2023, 169 patients within the HIV program were prescribed TAF/FTC/BIC treatment.

To date, few studies have been conducted in real-life conditions (19-22) to evaluate the effectiveness, safety, and clinical outcomes of TAF/FTC/BIC initiation, especially in patients at later stages of HIV, in everyday contexts. These outcomes are influenced by factors such as timely access to healthcare, follow-up, and proper adherence. No real-life studies have been conducted in Colombia, despite integrase inhibitors being the first-line treatment in the country and widely available as part of the mandatory health plan. Therefore, it is essential to evaluate the effectiveness, adherence, and clinical outcomes within our cohort. Generating our own data will allow us to create evidence with significant population impact.

Theoretical framework

Human Immunodeficiency Virus (HIV) is a retrovirus from the Retroviridae family,

specifically an enveloped positive-stranded RNA virus (5). There are two main types: HIV-1, the most common worldwide, and HIV-2, which is more prevalent in West Africa (23). The virus is transmitted through bodily fluids such as blood, semen, vaginal secretions, and breast milk. Once inside the body, HIV primarily targets CD4+ T lymphocytes of the immune system, binding to CD4 receptors and one of the chemokine co-receptors, CCR5 or CXCR4, to enter the host cell (6). This process of viral entry and replication leads to the progressive destruction of CD4+ T lymphocytes, resulting in severe immunodeficiency if not treated promptly (6,24).

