Bictegravir is a second-generation integrase strand transfer inhibitor (INSTI) used in HIV treatment. It is a key component of BikARVTy®, a fixed-dose regimen combining bictegravir, emtricitabine, and tenofovir alafenamide in a single daily tablet (52,53). This drug is notable for its high genetic barrier to resistance, meaning the virus is less likely to develop resistance to it compared to other INSTIs such as raltegravir and elvitegravir (54,55). It also has a limited drug-drug interaction profile, making it suitable for use in

combination with other antiretrovirals (52,56).

In phase 3 clinical trials, the bictegravir/emtricitabine/tenofovir alafenamide regimen has been shown to be non-inferior to dolutegravir-based regimens in both treatment-naïve and treatment-experienced patients, achieving effective virologic suppression without the emergence of resistance (53,57,58). Additionally, it is well tolerated and does not require prior HLA-B*5701 testing, which facilitates its rapid initiation in HIV treatment (53,57).

The most common adverse effects reported in clinical trials include diarrhea, nausea, and headache, with an incidence of at least 5% in treated subjects (59). Other less frequent adverse effects (\geq 2%) include fatigue, abnormal dreams, dizziness, insomnia, and abdominal distension (59). Regarding laboratory abnormalities, increases in serum creatinine, which stabilized throughout treatment, and increases in total bilirubin, mainly grade 1 and 2, were observed. Most adverse events were grade 1, and discontinuations due to adverse events were uncommon (59). Psychiatric events, such as suicidal ideation and depression, have also been reported, particularly in subjects with a history of psychiatric conditions. In subjects with end-stage renal disease, serious adverse events such as pneumonia and fluid overload were observed (59).

Objectives

General Objective: To estimate the clinical effectiveness and safety of HIV-positive patients on TAF/FTC/BIC treatment within an EPS in Colombia.

Specific Objectives:

- To characterize the sociodemographic and clinical profile of patients with HIV who initiate antiretroviral therapy with TAF/FTC/BIC.
- To identify the proportion of patients who have been on different pretreatment regimens before initiating TAF/FTC/BIC therapy.
- To assess the proportion of patients achieving virologic suppression at weeks 24

and 48 following the initiation of TAF/FTC/BIC therapy.

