Type of insurance	Insurance from the health system to whom the patient is covered.		0: Public 1: Private	
Residence department	Department of Colombia where the patient lives	Qualitative	Text	
AHT	Patient with hypertension marked in electronic medical record	Qualitative	0: No 1: Yes	
Diabetes Mellitus	Patient with diabetes marked in electronic medical record	Qualitative	0: No 1: Yes	
Chronic kidney disease	Patient with chronic kidney disease marked in electronic medical record	Qualitative	0: No 1: Yes	
Hepatitis B co-infection	Patient with repeated confirmed ICD-10 diagnosis of B181 Chronic type B viral hepatitis, no delta agent from the date of HIV diagnosis to the end of follow-up.	Qualitative	0: No 1: Yes	
Hepatitis C co-infection	Patient with repeated confirmed ICD-10 diagnosis of B182 Chronic viral hepatitis type C from the date of HIV diagnosis to the end of follow-up.	Qualitative	0: No 1: Yes	
Major depressive disorder	Patient with confirmed ICD-10 repeat diagnoses: F320, F321, F322, F323, F328, F329, F330, F331, F332, F333, F334, F338, F339, F340, F341, F348, F349, F380, F381, F388 or F39X from the date of HIV diagnosis to the end of follow-up		0: No 1: Yes	
Start date TAF/FTC/BIC	Medication start date TAF/FTC/BIC	Quantitative, continuous	dd/mm/yyyy	
End date TAF/FTC/BIC	Medication end date TAF/FTC/BIC	Quantitative, continuous	dd/mm/yyyy	
NAIVE for TAF/FTC/BIC	Patient whose first HIV treatment is TAF/FTC/BIC	Qualitative	0: No 1: Yes	
ARVT scheme prior to TAF/FTC/BIC	Name of ARVT scheme immediately preceding TAF/FTC/BIC used for HIV treatment	Qualitative	Text	
HIV viral load at baseline	The patient has HIV viral load results at baseline (+ or - 4 weeks) of TAF/FTC/BIC therapy.	Qualitative	0: No 1: Yes	
BHIV viral load at baseline value	HIV viral load value at baseline (+ or - 4 weeks) of TAF/FTC/BIC therapy	Quantitative, continuous	1, 1.5, 1.8, 2, n	
HIV viral load at week 24	The patient has HIV viral load results at week 24 (+ or - 2 weeks) of TAF/FTC/BIC therapy.	Qualitative	0: No 1: Yes	
HIV viral load value at week 24	HIV viral load value at week 24 (+ or - 2 weeks) of TAF/FTC/BIC therapy	Quantitative, continuous	1, 1.5, 1.8, 2, n	
HIV viral load at week 48	The patient has HIV viral load results at week 48 (+ or - 2 weeks) of TAF/FTC/BIC therapy.	Qualitative	0: No 1: Yes	
HIV viral load value at week 48	HIV viral load value at week 48 (+ or - 2 weeks) of TAF/FTC/BIC therapy	Quantitative, continuous	1, 1.5, 1.8, 2, n	

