Number of medication claims	Number of TAF/FTC/BIC medication claims during the 48-week follow-up	Quantitative, discrete	1, 2, 3, n
Headache emergency	nergency The patient visited the emergency department during the period of TAF/FTC/BIC use for ICD-10 codes G444 and/or G448		0: No 1: Yes
Diarrhea emergency	The patient visited the emergency department during the period of TAF/FTC/BIC use for ICD-10 code A09X: Diarrhea and gastroenteritis of presumed infectious origin	ing the period of or ICD-10 code A09X: Qualitative enteritis of presumed	
Nausea and vomiting emergency	The patient visited the emergency department during the period of TAF/FTC/BIC use for ICD-10 code R11X: Nausea and vomiting	Qualitative	0: No 1: Yes
Termination of health insurance coverage	The patient terminated their health insurance with EPS SURA.	Qualitative	0: No 1: Yes
Date of termination of insurance coverage	Date of termination of health insurance with EPS SURA	Quantitative, continuous	dd/mm/yyyy
Death	The patient passed away after the index date	Qualitative	0: No 1: Yes
Date of death	Date of death Date of patient's death		dd/mm/yyyy

Sample Size

No sampling will be conducted, as data from the entire population (census) that meets the eligibility criteria for this study will be used.

Statistical Analysis

The database created in Access will be transferred to RStudio and Jamovi for the corresponding descriptive analysis.

Characterization of the Sociodemographic and Clinical Profile

Absolute and relative frequencies will be calculated for categorical variables. For numerical variables, normality will be assessed using the Shapiro-Wilk test. Variables with a p-value greater than 0.05 will be considered to follow a normal distribution and will be represented by means and standard deviations. For variables that do not follow a normal distribution, medians and interquartile ranges will be used.

Proportion of Pretreatment Regimens

The proportion of patients who have received different combinations of ART prior to starting TAF/FTC/BIC will be calculated. Frequency tables will be used to display the proportion of each pretreatment regimen, supplemented by bar charts reflecting the frequencies of the most common treatments.

Virologic Suppression at 24 and 48 Weeks

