Virologic suppression is defined as a viral load of <50 copies/mL at weeks 24 and 48 of treatment. The proportion of patients achieving this threshold will be calculated at both time points, and the results will be compared between weeks 24 and 48 using McNemar's test for related samples.

Effective Access to Treatment

Effective treatment is defined as the initiation of therapy within a reasonable time after prescription. The time between prescription and the initiation of treatment will be calculated (mean or median, depending on the normality test), and patients will be classified into two categories: those who initiate treatment effectively (within a short period, generally defined as initiation within 7-14 days of HIV diagnosis) and

those who experience delays.

Paraclinical Results: CD4 T-Lymphocytes, Renal Function, and Lipid Profile

To describe changes in clinical markers at weeks 24 and 48, the summary measure (mean or median, depending on the normality test) of baseline values will be compared with the values of these biomarkers at the two time points. Paired-samples t-tests or Wilcoxon tests will be used if the data distribution is non-normal.

Rapid Onset of Therapy

The frequency of patients meeting this criterion will be calculated, and the characteristics of those with rapid onset versus those without will be compared using the chi-square test.

Treatment-Related Adverse Events

Treatment-related adverse events at weeks 24 and 48 will be characterized and classified according to type and severity. The proportion of patients experiencing these events will be calculated and compared between the two time points. Contingency tables and chi-square tests will be used to analyze the relationship between adverse events and other clinical and sociodemographic variables.

Adherence to Treatment

Adherence will be measured using pharmacy claims information with the Proportion of Days Covered (PDC). PDC calculates the proportion of days the patient has access to the medication over a specified period (64,65). In this study, patients with a PDC of 80% or higher will be considered to have adequate adherence. However, studies have shown that even lower adherence levels can still result in a high rate of viral suppression.

Biases

The following biases are considered potential risks in this study:

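### The TAF/FTC/BIC end date is collected without a reason, so late stops for intolerance are not marked as adverse events and early ones leave the cohort

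*Combined protocol and SAP*

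**What the plan says.** All places are in the combined protocol and SAP.

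- **Variables, treatment rows.** The end of treatment is recorded as "Medication end date TAF/FTC/BIC", in date format. The neighbouring regimen field looks backward only: "Name of ARVT scheme immediately preceding TAF/FTC/BIC used for HIV treatment". No row gives a reason for stopping or the regimen that followed.
- **Variables, clinical event rows.** There are three emergency-visit flags. Headache is a visit to the emergency "department during the period of TAF/FTC/BIC use for ICD-10 codes G444 and/or G448". Diarrhea uses the code for "Diarrhea and gastroenteritis of presumed infectious origin". The third reads "The patient visited the emergency department during the period of TAF/FTC/BIC use for ICD-10 code R11X: Nausea and vomiting". None carries causality or severity.
- **Variables, other relevant rows.** Loss of coverage and death each have a flag and a date. AST, ALT, bilirubin, creatinine and eGFR are taken at baseline and weeks 24 and 48.
- **Exclusion Criteria.** Patients who change provider or stop the regimen within the first six months are not included.
- **Statistical Analysis, Treatment-Related Adverse Events.** "Treatment-related adverse events at weeks 24 and 48 will be characterized and classified according to type and severity". The proportion of patients with an event is then to be calculated and compared between the two time points. No rule derives this outcome from the listed variables, and no analysis treats stopping as an outcome.
- **HIV Treatment.** Among the safety findings from the product's trials, the protocol notes that "discontinuations due to adverse events were uncommon".

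**The concern.** Safety is part of the general objective, and a specific objective promises the proportion of treatment-related adverse events at weeks 24 and 48. Stopping a drug because it is not tolerated is a direct expression of such an event. The plan records when treatment stopped but not why, so it cannot separate intolerance from a stop for interaction, supply or the patient's own decision.

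The emergency-visit flags are unlikely to fill the gap. The HIV Treatment section says that most adverse events with this regimen were grade 1, and it lists fatigue, abnormal dreams, dizziness, insomnia and psychiatric events. Any of these could end treatment without an emergency visit for one of the three coded symptoms. The depression variable does not help: it runs from HIV diagnosis, not from the start of the drug.

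At stake is an adverse-event proportion that omits intolerance serious enough to end treatment, in a study that would then describe the regimen as well tolerated.

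**Working it through.** The plan states no adverse-event rate, number of stops or analysed sample size, so there is no figure to reproduce. The check sets the variable table against the exclusion rule and then sizes each route.

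**Inputs**

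- 169 patients were prescribed the regimen from 2020 to 2023 (Problem Statement and Relevance). This is before exclusions.
- The study takes a census of those eligible (Sample Size), so the analysed n is unknown. I assume 169, 150 and 120 to show a range.
- The laboratory windows for weeks 24 and 48 are plus or minus 2 weeks (Variables).
- Stops before six months are excluded (Exclusion Criteria).

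**Step 1. Which stops stay in the cohort?**

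- Week 24 is 24 × 7 = day 168, and its window closes at 26 × 7 = day 182.
- Six months is 365.25 / 2 = 182.6 days.
- Week 48 is 48 × 7 = day 336, and its window closes at day 350.

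A patient who stops before about day 183 is therefore excluded. A retained patient can stop only after the week-24 window has closed. The two routes are separate:

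| Time of stop for intolerance | Emergency visit for a listed symptom | What the plan does |
|---|---|---|
| Before about day 183 | Yes or no | Excluded: out of numerator and denominator |
| After about day 183 | Yes | Retained, one flag set |
| After about day 183 | No | Retained, no variable marks an event |

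**Step 2. Late stops (week-48 proportion)**

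With x recorded events and k missed stops among n patients, the plan reports x/n where (x + k)/n is wanted. The shortfall is k/n, so each missed patient costs 100/n points:

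- n = 169: 0.59 points
- n = 150: 0.67 points
- n = 120: 0.83 points

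Take n = 169 and x = 0. The report would read 0% (exact 95% interval 0 to 2.2%). With k = 3 it should read 1.8% (0.4 to 5.1%), and with k = 8, 4.7% (2.1 to 9.1%).

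**Step 3. Early stops (lost by exclusion)**

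With e early intolerance stops among N = 169 and no other events, the wanted figure is e/169 and the reported figure is 0/(169 − e):

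- e = 2: 1.2%, reported as 0 of 167
- e = 5: 3.0%, reported as 0 of 164
- e = 8: 4.7%, reported as 0 of 161

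For e = 5, the exact upper limit on 0 of 164 is 1 − 0.025^(1/164) = 2.2%. The reported interval would not contain the 3.0% among all who started.

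**Step 4. What the added field would allow**

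Among 169 initiators, 0 stops for adverse events would give an upper 95% limit of 2.2%; 2 stops would give 1.2% (0.1 to 4.2%); 5 stops would give 3.0% (1.0 to 6.8%). These show the precision available, not the size of the bias. The counts are illustrative.

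**The case against.** A reader might infer that every patient who stops for intolerance without an emergency visit is scored as event-free. The documents do not support that. Those who stop before six months are removed by the exclusion criteria, so they are not counted as event-free; they are not counted at all. For them the problem is selection, and a reason field alone would not cure it. The misclassification is confined to later stops and the week-48 figure. This objection stands.

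Other parts of the opposing case also stand:

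- Not all stops look alike in the data. Loss of coverage and death are dated and can be matched to the end date. Pregnancy and virologic failure are exclusion criteria, and viral load is extracted at weeks 24 and 48. What cannot be separated is mainly intolerance, interaction, supply and patient decision.
- The safety data are wider than three symptoms. Liver and renal values and death are collected, so an intolerance visible in the laboratory might show, although no rule turns a value into an event.
- That an unmarked patient counts as having no event is inferred from the variable list, because the plan gives no derivation rule.
- It would be tempting to say that the study forfeits a comparison with published discontinuation figures. The protocol gives no such figure, only that these stops were uncommon.
- The documents do not establish that charts always hold the reason. The statement "Program indicators include treatment abandonment rates" shows that the programme follows stopping, not that it records why.

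None of this supplies a variable that would identify a stop for intolerance.

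**Conclusion.** The point holds in a limited form. After six months, a stop for intolerance without one of the three emergency visits leaves no mark in the data and can lower the week-48 proportion, by 0.59 points per patient at n = 169 and 0.83 at an assumed n = 120. Before six months, the patient leaves the cohort, and 5 such stops among 169 would be reported as 0 of 164.

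This rests on three assumptions: the adverse-event outcome is built from the listed variables; the week-48 proportion counts events up to that week; and six months means about 183 days. If six months is taken as 180 days, a stop on days 180 to 182 would fall in the last days of the week-24 window, which hardly changes the conclusion. The true number of stops is unknown and may be small. Since the expected event rate is low, a few would still be enough to change how the safety result reads. The change should be made; without it the study can still report its other outcomes.

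**What to change.** 1. Add one coded field, reason for ending TAF/FTC/BIC: adverse event, interaction, supply, patient decision, other, unknown. Cross-check coverage loss and death against their existing dates. Fill it from the chart for every initiator with an end date, including those who stop before six months.
2. State in the Treatment-Related Adverse Events section that a stop for an adverse event counts as a treatment-related event.
3. Report the number stopping for an adverse event by weeks 24 and 48, with exact binomial intervals, in a safety denominator of all initiators who meet the other criteria. Early stoppers are kept for this analysis only, or reported beside the main cohort. Give separately the number who changed provider before six months, since their later stops cannot be seen.

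The cost is a small amount of extra chart abstraction, plus some reasons coded unknown, whose number should be reported. Early stoppers must be identified anyway to apply the exclusion. The Data Collection Plan provides for a manual search of records, but also says that unstructured data will be converted by automated means alone. That section should state that this field is abstracted by hand.

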- B227: HIV disease resulting in multiple illnesses classified elsewhere.
- B230: Acute HIV infection syndrome.
- B231: HIV disease resulting in generalized lymphadenopathy (persistent).
- B232: HIV disease resulting in immunologic and hematologic abnormalities, not elsewhere classified.
- B238: HIV disease resulting in other specified conditions.
- B24X: Human immunodeficiency virus (HIV) disease, not otherwise specified.
- F024: Dementia in human immunodeficiency virus (HIV) disease (B22.0†).
- Z21X: Asymptomatic human immunodeficiency virus (HIV) infection status.

All information on the variables of interest will be extracted from the clinical records. The process of data collection and form completion will be carried out by personnel from the Clinical Research Unit, following training to ensure standardized data capture. Quality

control of the data will be performed, including the review of codes, missing data, and any incorrect or improperly transcribed characters, according to the variable, by the researchers before the dataset is purified for analysis.

Study Population

All patients who meet the defined selection criteria within the established time frame for the search will be included:

- Inclusion Criteria:
 - Male or female patients aged 18 years or older.
 - Individuals with a confirmed HIV diagnosis.
 - Individuals enrolled in EPS SURA during the study period.
 - Patients receiving treatment with the TAF/FTC/BIC regimen.
- Exclusion Criteria:
 - Patients with a concurrent diagnosis of tuberculosis.
 - Pregnant patients during the study period.
 - Patients with virologic failure.
 - Patients who started treatment with TAF/FTC/BIC but changed providers or discontinued treatment before completing six months of therapy.

Variables

Variable Name	Definition	Nature	Measuring Level
Primary diagnosis of HIV	Patient with primary ICD-10 diagnosis of: B200, B201, B202, B203, B204, B205, B206, B207, B208, B209, B210, B211, B212, B213, B217, B218, B219, B220, B221, B222, B227, B230, B231, B232, B238, B24X, F024 or Z21X	Qualitative	Text
Diagnosis date	Date of first confirmed repeat HIV diagnosis recorded in the medical record	Quantitative, continuous	dd/mm/yyyy
Date of birth	Patient's date of birth	Quantitative, continuous	dd/mm/yyyy
Sex	Sex defined by patient's medical history	Qualitative	0: Female; 1: Male.
Race	Race defined by patient's medical history	Qualitative	Texto

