Total bilirubin at week 48	The patient has total bilirubin results at week 48 (+ or – 2 weeks) of TAF/FTC/BIC therapy	Qualitative	0: No 1: Yes	
Total bilirubin value at week 48	Total bilirubin value at week 48 (+ or – 2 weeks) of TAF/FTC/BIC therapy	Quantitative, continuous	1, 1.5, 1.8, 2, n	
Serum creatinine at baseline	The patient has baseline serum creatinine results (+ or – 4 weeks) of TAF/FTC/BIC therapy	Qualitative	0: No 1: Yes	
Serum creatinine value at baseline	Baseline serum creatinine value (+ or – 4 weeks) of TAF/FTC/BIC therapy	Quantitative, continuous	1, 1.5, 1.8, 2, n	
Serum creatinine at week 24	The patient has serum creatinine results at week 24 (+ or – 2 weeks) of TAF/FTC/BIC therapy	Qualitative	0: No 1: Yes	
Serum creatinine value at week 24	Serum creatinine value at week 24 (+ or – 2 weeks) of TAF/FTC/BIC therapy	TAF/FTC/BIC therapy continuous		
Serum creatinine at week 48	The patient has serum creatinine results at week 48 (+ or – 2 weeks) of TAF/FTC/BIC therapy Serum creatinine value at week 48 (+ or – 2	Qualitative	0: No 1: Yes	
Serum creatinine value at week 48	Quantitative, continuous	1, 1.5, 1.8, 2, n		

Glomerular filtration rate at baseline	The patient has the estimated glomerular filtration rate (eGFR) by CKD-EPI at baseline (+ or - 4 weeks) of TAF/FTC/BIC therapy	Qualitative	0: No 1: Yes
Value of glomerular filtration rate at baseline	Value of estimated glomerular filtration rate (eGFR) calculated by CKD-EPI at baseline (+ or - 4 weeks) of TAF/FTC/BIC therapy	Quantitative, continuous	1, 1.5, 1.8, 2, n
Glomerular filtration rate at week 24	The patient has an estimated glomerular filtration rate (eGFR) calculated by CKD-EPI at week 24 (+ or - 2 weeks) of TAF/FTC/BIC therapy	Qualitative	0: No 1: Yes
Glomerular filtration rate value at week 24	Value of estimated glomerular filtration rate (eGFR) calculated by CKD-EPI at week 24 (+ or - 2 weeks) of TAF/FTC/BIC therapy	Quantitative, continuous	1, 1.5, 1.8, 2, n
Glomerular filtration rate at week 48	The patient has the estimated glomerular filtration rate (eGFR) calculated by CKD-EPI at week 48 (+ or - 2 weeks) of TAF/FTC/BIC therapy	Qualitative	0: No 1: Yes
Glomerular filtration rate value at week 48	Value of estimated glomerular filtration rate (eGFR) calculated by CKD-EPI at week 48 (+ or - 2 weeks) of TAF/FTC/BIC therapy	Quantitative, continuous	1, 1.5, 1.8, 2, n

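### eGFR is listed as a record item separate from creatinine, with no rule to compute it and no CKD-EPI version; computing it once from data already collected is a free improvement

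*Combined protocol and SAP*

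**What the plan says.** In the Variables table, eGFR has two entries at each of baseline, week 24 and week 48: a yes/no item for whether a result exists, and a value. The baseline availability item is "The patient has the estimated glomerular filtration rate (eGFR) by CKD-EPI at baseline (+ or - 4 weeks) of TAF/FTC/BIC therapy", and the value is defined as "Value of estimated glomerular filtration rate (eGFR) calculated by CKD-EPI at baseline (+ or - 4 weeks) of TAF/FTC/BIC therapy". The week 24 and week 48 values are defined in the same way, with a window of 2 weeks either side.

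Serum creatinine has the same layout and the same windows. Its baseline entries begin "The patient has baseline serum creatinine results" and "Baseline serum creatinine value". The table also collects sex and date of birth ("Patient's date of birth").

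On sourcing, the Data Collection Plan states: "All information on the variables of interest will be extracted from the clinical records".

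Renal function at weeks 24 and 48 is one of the specific objectives. The Statistical Analysis section on paraclinical results compares baseline with each later time point by paired t-test or Wilcoxon test. It does not say whether renal function there means creatinine, eGFR or both.

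**The concern.** eGFR by CKD-EPI is not a separate measurement. It is a function of creatinine, age and sex, and the plan already collects what is needed to compute it. Treating it as a laboratory result that may or may not be present has two possible consequences.

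First, a visit with creatinine but no recorded eGFR counts as missing for eGFR. A paired test needs both visits, so one such gap removes the pair. The creatinine and eGFR results could then describe different subsets of a cohort that has at most 169 patients before exclusions.

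Second, the Problem Statement says that follow-up is spread over specialised institutions and affiliated providers. Nothing requires them to have used the same CKD-EPI version, or a patient's two values to share one. A change of version between visits would enter the paired difference although creatinine had not changed.

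**Working it through.** **Step 1. What the plan fixes and what it leaves open.** It names CKD-EPI at all three visits. It does not say who performs the calculation, which version applies, or what happens when creatinine is present and eGFR is not.

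**Step 2. Which reading fits the table.** If the study team computed eGFR, it would exist whenever creatinine did, because birth date and sex are collected for every patient. An eGFR flag would then repeat the creatinine flag. A separate flag has a purpose only if eGFR can be absent when creatinine is present. Together with the sourcing sentence in the Data Collection Plan, this makes transcription from the record the natural reading.

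**Step 3. Whether existing checks would catch it.** The cleaning rules cover coherence, completeness, valid range and duplication. The 10% review under Biases compares the database with the chart. An eGFR copied correctly from a record that used another CKD-EPI version passes both.

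**Step 4. Possible loss of pairs.** The documents give no availability rate for eGFR, so there is no figure of the plan's to reproduce. Let *a* be the share of creatinine results that come with a recorded CKD-EPI eGFR. This is an assumption, taken as equal at both visits, among patients with creatinine at both. The share of creatinine pairs that also have an eGFR pair is:

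- at least max(0, 2a − 1), when the gaps at the two visits fall on different patients;
- a², when gaps at the two visits are independent;
- at most *a*, when the gaps fall on the same patients.

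The width of an interval for the mean change grows by 1/√(share) relative to using all creatinine pairs. Pair counts use 169, the number prescribed the regimen in 2020 to 2023, and assume complete creatinine. They are therefore upper limits before exclusions.

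| a (assumed) | Share: lower / independent / upper | Pairs of 169 | Width factor |
|---|---|---|---|
| 1.00 | 1.00 / 1.00 / 1.00 | 169 / 169 / 169 | 1.00 / 1.00 / 1.00 |
| 0.95 | 0.90 / 0.9025 / 0.95 | 152 / 153 / 161 | 1.05 / 1.05 / 1.03 |
| 0.90 | 0.80 / 0.81 / 0.90 | 135 / 137 / 152 | 1.12 / 1.11 / 1.05 |
| 0.80 | 0.60 / 0.64 / 0.80 | 101 / 108 / 135 | 1.29 / 1.25 / 1.12 |
| 0.70 | 0.40 / 0.49 / 0.70 | 68 / 83 / 118 | 1.58 / 1.43 / 1.20 |

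For example, at a = 0.80: 2 × 0.80 − 1 = 0.60; 0.80² = 0.64; 1/√0.64 = 1.25.

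**Step 5. After the fix.** Every patient with creatinine at both visits has an eGFR pair, so the share is 1 whatever the value of *a*. One version applied throughout makes the effect of a version change zero by construction.

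**Step 6. Size of a version effect.** It cannot be computed here. The documents contain neither the CKD-EPI formula nor any record of which version a provider used, so no figure is given.

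**The case against.** The strongest reply is that the plan is silent here rather than wrong. The value definitions speak of eGFR calculated by CKD-EPI without saying by whom, and an eGFR that the team computes from a charted creatinine would still come from clinical records. That is fair. A reader might infer that the sponsor has decided against computing eGFR; the text does not say so. It only makes transcription the more natural reading.

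Three further inferences are tempting and not supported:

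- **That patients will be lost.** Loss occurs only where creatinine is present and no CKD-EPI eGFR is recorded. If providers always report the two together, it is zero. If a provider consistently reports or omits eGFR, the loss lies near the mild end of the range. Creatinine remains available as a renal marker in any case, so the renal objective does not lose these patients altogether.
- **That different equations will be mixed.** CKD-EPI is required at every visit, so a value from another equation does not meet the definition. Only the version is open.
- **That a shift of a particular size will appear in eGFR.** Any such figure would need formulas, and a change of version in these records, that the documents do not show.

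It is also true that the study is a descriptive census with no sample size or decision resting on eGFR, which limits the weight of the point. What survives is that a better method is available at once. Provided that the creatinine behind each recorded eGFR is in the record, computing cannot yield fewer pairs than transcribing.

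**Conclusion.** The point holds as a minor improvement. As written, the creatinine and eGFR comparisons can rest on different patients, and the CKD-EPI version is not controlled across providers or visits. The loss of pairs is unknown and may be zero. Under the assumed availability shares it runs from 5% to 10% of creatinine pairs at 95%, and from 20% to 40% at 80%. No magnitude is claimed for version differences. The conclusion rests on reading the separate flag as a sign of transcription. On the other reading, the plan still needs to say who computes eGFR and with which version.

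**What to change.** State in the Variables section that eGFR is computed by the study team at every visit with a creatinine value, using one named CKD-EPI version, the recorded sex, and age at the sample date. The table lists no sample date. Either add it or use age at the nominal visit date (the index date, or the index date plus 24 or 48 weeks); the windows are a few weeks at most, so age barely changes. Drop the three eGFR availability flags, since the creatinine flags then serve both markers. Keep any eGFR found in the record only as a check on the computed value. In the analysis section, say whether the renal comparison uses creatinine, eGFR or both.

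The cost is one formula in the analysis code, with three fewer flags to complete. As the study is retrospective, this can be settled at any time before the analysis.
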